Therefore, alternate methods of providing tight V_T control during PPV in the delivery room resuscitation of preterm infants is needed, given the complex interaction of mask leak, lung compliance, PIP, and resuscitator skill. Using VTV immediately after birth would provide continuity from the delivery room into the NICU. Tracy et al. compared mask PPV with a T-Piece or VTV during simulated neonatal resuscitation and reported a lower coefficient of variations and lower V_T delivery with ventilator driven VTV compared PPV with a T-Piece (29). Similarly, Jain et al. compared VTV via a mechanical ventilator to manual T-Piece PPV and reported improved volume targeting at different compliance settings and a reduction in mask leak during simulated mask ventilation

Abbreviations

WCHRI, women and children's health research institute; PPV, positive pressure ventilation; V_T , tidal volume; PIP, peak inflation pressure; VTV, volume-targeted ventilation; RFM, respiratory function monitor; HIE, hypoxic-ischemic encephalopathy; IVH, intraventricular hemorrhage; PVL, periventricular leukomalacia; NICU, neonatal intensive care unit; ROP, retinopathy of prematurity; SAE, severe adverse event; DSMB, data safety monitoring board; SURG-TLX, surgery task load index; VOLT, volume targeted mask ventilation versus pressure ventilation in preterm infants trial.

(30). These studies suggest that VTV is feasible at least during animal or simulated neonatal resuscitation. Furthermore, Menakaya et al. compared VTV with a PPV using a Flow-Inflating bag and reported that preterm infants can be safely and effectively resuscitated using a ventilator (31). However, no study has compared VTV with T-Piece resuscitator during neonatal resuscitation of preterm infants in the delivery room. Thus, a clinical trial using VTV in the delivery room is urgently needed to determine if (a) this method can be feasibly used in the delivery room and (b) can potentially improve outcomes by reducing bronchopulmonary dysplasia and brain injury in preterm infants.

Objectives

Primary objective

To determine feasibility and safety of a trial comparing VTV-PPV to PPV in extremely preterm infants.

Secondary objectives

To evaluate clinical outcomes and HCP experience of the VTV-PPV.

Primary research question

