Population: In preterm infants born at 23⁰–28⁶ weeks' gestation is a trial of **Intervention:** mask ventilation using a mechanical ventilator (VTV-PPV) **Comparison:** compared to mask ventilation using a T-Piece Resuscitator (PPV) **Outcome:** feasible during mask ventilation in the delivery room, which will be assessed by percentage of eligible participants (=infants requiring PPV) randomized to the VTV group and receive the allocated intervention without protocol deviation (i.e., without crossover to the control group) **Timeline:** during the first 10 min after birth?

Secondary research questions

1. In preterm infants born at 23⁰–28⁶ weeks of gestation, does mask ventilation using a mechanical ventilator compared to mask ventilation using a T-Piece Resuscitator reduce neonatal morbidities (severe brain injury, bronchopulmonary dysplasia; and severe retinopathy of prematurity) and reduce the number of infants requiring intubation in the delivery room by transitioning more successfully to CPAP.
2. What qualitative feedback do HCPs have on the experience of using VTV-PPV in the delivery room?
3. How does VTV-PPV compared with PPV affect subjective workload reported by HCPs performing mask ventilation?

Trial design

A single centre randomized controlled trial.

Methods: participants, interventions, outcomes

Study setting

Royal Alexandra Hospital, Edmonton, Canada, a tertiary perinatal center admitting ~140 infants born between 23⁰ to 28⁶ weeks' gestation annually. The trial is registered on [clinicaltrials.gov](https://clinicaltrials.gov/study/NCT05144724) (<https://clinicaltrials.gov/study/NCT05144724>) (Table 1).

Eligibility criteria

Inclusion criteria (all must be satisfied)

- Born between 23⁰/⁷ to 28⁶/⁷ weeks' gestation based on best obstetrical estimates
- Considered suitable for full resuscitation, i.e., no parental request or antenatal decision to forego resuscitation
- Deferred parental consent post-intervention

Exclusion criteria

- Major congenital or chromosomal malformation
- Conditions that might have an adverse effect on breathing or ventilation (e.g., high risk for lung hypoplasia, congenital diaphragmatic hernia)
- Antenatally detected congenital heart disease requiring intervention in the neonatal period
- Antenatally diagnosed Hydrops requiring intervention in the neonatal period
- Neonatal resuscitation initiated before NICU team arrival
- Infants who are born outside of study center and transported to center after delivery

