7. Duration of any respiratory support (invasive mechanical ventilation, non-invasive ventilation with continuous positive airway pressure, nasal intermittent positive pressure ventilation, or non-invasive neural assist ventilation or non-invasive high frequency ventilation, or high-flow nasal cannula) in days
8. Duration of supplemental oxygen in days
9. Length of hospital stay in days
10. Rate of intubation in the delivery room
11. Rate of chest compression in the delivery room
12. Rate of pneumothorax (diagnosed by chest x-ray or lung ultrasound) and interventions (e.g., needle drainage or chest drain)
13. Necrotizing enterocolitis, Modified Bell's criteria stage 2 or greater (37)
14. Duration of positive pressure ventilation at birth (within the first 10 min)
15. Resuscitators subjective workload performing mask ventilation, as evaluated by Surgery Task Load Index (SURG-TLX)-questionnaire.

16. Resuscitators qualitative feedback on using VTV-PPV in the delivery room, provided through free text responses.

neonatal deliveries will open an envelope with the group assignment and will enroll participants.

Participant timeline

Sample size

This will be a trial to assess the feasibility of VTV-PPV in the delivery room. Our primary outcome will assess the percentage of eligible participants (=infants requiring PPV) who have the intervention performed correctly without protocol deviation (=cross over to control group when randomized to VTV-group). We aim to recruit a sample of 50 infants (25 per arm) randomized 1:1 to VTV-PPV or PPV. The proposed sample size should be reached within 24 months. This study will be an initial trial for a large multi-center trial.

Recruitment

The study will be carried out at the Royal Alexandra Hospital, Edmonton, Canada, a tertiary perinatal center with ~6,000 deliveries annually admitting ~140 infants born between 23^{+0} to 28^{+6} weeks' gestation annually. Approximately 60% of babies born between 23 and 28 weeks' gestation require PPV at birth. The study site has a long history of conducting randomized trials and has the proven capability of enrolling the required number of infants. The number of infants being recruited will be 50, as per sample size. The overall recruitment period is a maximum of 24 months. There will be 50 infants recruited in Canada.

Assignment of interventions

Allocation

Sequence generation

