Participant data will be handled in compliance with applicable data protection and privacy regulations. All data will be securely stored, with electronic records accessible only to authorized research team members via password protection. Data will be de-identified, and participant anonymity will be maintained in all scientific publications and presentations.

Biological specimens

There will be no biological specimens collected.

Statistical methods

Statistical methods for primary and secondary outcomes

WCHRI will handle, verify, and analyze VOLT-trial data, with statistical methods aligned to standard randomized trial practices. Results will be reported in compliance with CONSORT guidelines.

The primary analysis will be conducted using an “intention-to-treat” approach. The primary analysis will focus on feasibility defined as percentage (75% or greater) of eligible participants (=infants requiring PPV) who have the intervention performed correctly without protocol deviation (=cross over to control group when randomized to VTV-group). Analysis of secondary outcomes will include the above-mentioned secondary outcomes using descriptive statistics. Summary statistics will be presented for baseline and clinical characteristics; continuous data by mean, two-sided 95%CI of the mean, standard deviation, median, interquartile range (first and third quartiles), minimum and maximum. Categorical data will be presented by absolute and relative frequencies. The clinical characteristics and outcome parameters will be compared using Student’s *t*-test for parametric and Mann-Whitney *U*-test for nonparametric comparisons of continuous variables, and χ^2 for categorical variables. The analysis will be 2-sided and *p*-value <0.05 will be considered statistically significant.

Interim safety analyses

The DSMB will conduct one interim safety analyses throughout the trial to assess in-hospital mortality and SAEs after 24 (50%) infants recruited.

Methods for additional analyses (e.g., subgroup analyses)

At the end of each intervention, the clinician’s workload will be assessed using the Surgery Task Load Index (SURG-TLX)-questionnaire (40). The SURG-TLX- questionnaire is a multidimensional workload measure to assess the impact of six various sources of stress on the perceived demands of trained healthcare professionals. These six aspects are then combined into a total workload score.

The SURG-TLX- questionnaire will assess:

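### Secondary outcomes of a 25-per-arm feasibility trial carry a p<0.05 significance rule with no statement that the comparisons are exploratory or unadjusted

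*Protocol*

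**What the plan says.** All of this is in the protocol.

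- **Statistical methods for primary and secondary outcomes.** The primary analysis is a feasibility percentage, with 75% or greater as the criterion. For the rest, "Analysis of secondary outcomes will include the above-mentioned secondary outcomes using descriptive statistics". Later in the same paragraph, "The clinical characteristics and outcome parameters will be compared using" a t-test, a Mann-Whitney test or a chi-squared test, and a two-sided p-value "<0.05 will be considered statistically significant". The only confidence interval promised is for the mean of continuous data.
- **Primary research question.** The percentage is taken among infants "randomized to the VTV group and receive the allocated intervention without protocol deviation", so it concerns one arm.
- **Sample size.** "This will be a trial to assess the feasibility of VTV-PPV in the delivery room", and "We aim to recruit a sample of 50 infants (25 per arm) randomized 1:1". No power, effect size or precision is given.
- **Objectives.** Primary: "To determine feasibility and safety of a trial comparing VTV-PPV to PPV in extremely preterm infants". Secondary: "To evaluate clinical outcomes and HCP experience of the VTV-PPV". Secondary question 1 asks whether VTV-PPV reduces morbidities. Question 3 asks about workload.
- **Background, on adjusting tidal volume.** Earlier randomized trials are criticised because brain injury was an unpowered secondary outcome, so their results may be chance.

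**The concern.** The paragraph begins with a descriptive plan and ends with a verdict rule. The rule has nothing to act on except the secondary outcomes and the clinical characteristics, since the primary outcome has no between-arm contrast. Followed as written, it sorts death, brain injury, BPD, ROP and the other secondary outcomes into significant and not significant with 25 infants per arm.

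Both labels can mislead. Not significant would be the usual result even for a real effect of the size the protocol cites. Significant would come with an inflated estimate, or could be one chance result among many tests. The Discussion says the findings should inform a definitive trial. For that purpose event rates and differences with their uncertainty are useful, and a significance label is not. The protocol makes the same criticism of earlier trials.

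**Working it through.** The protocol gives no power calculation to reproduce. Only 2 × 25 = 50 can be checked, and it agrees.

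**1. What the rule can apply to.** The primary outcome is the share of VTV-arm infants treated without crossover, set against 75%. It has no comparison with the PPV arm. The compared outcome parameters are therefore the secondary outcomes. Sixteen are listed, and the last is free text on VTV-PPV, which leaves 15 testable items.

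**2. Effects used for scale.** The background cites a NICU meta-analysis with relative risks (RR) and numbers needed to treat (NNT). Implied control risk = (1/NNT)/(1 − RR); treated risk = RR × control risk.

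| Outcome | RR, NNT | Control | Treated | Gap |
|---|---|---|---|---|
| Pneumothorax | 0.46, 17 | (1/17)/0.54 = 10.9% | 5.0% | 5.9 points |
| Death or BPD | 0.73, 8 | (1/8)/0.27 = 46.3% | 33.8% | 12.5 points |
| PVL or grade 3–4 IVH | 0.48, 11 | (1/11)/0.52 = 17.5% | 8.4% | 9.1 points |

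**3. Power and overstatement.** Exact enumeration of all tables with 25 per arm, uncorrected chi-squared test, two-sided 0.05:

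| Outcome | Power | Mean absolute gap when p<0.05 | Ratio to true gap |
|---|---|---|---|
| Pneumothorax | 10.0% | 19.3 points | 3.3 |
| Death or BPD | 16.7% | 33.1 points | 2.6 |
| PVL or grade 3–4 IVH | 16.4% | 22.9 points | 2.5 |

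**4. Smallest significant gap.** 0 vs 3 infants gives p = 0.074; 0 vs 4 gives p = 0.037. No table with a smaller gap reaches p<0.05. The minimum is therefore 4/25 = 16 points, above all three gaps in step 2. With more events the gap must be larger: 4 vs 10 gives p = 0.059 and 4 vs 11 gives p = 0.031, which is 7 infants or 28 points.

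**5. False positives.** With 15 independent tests at nominal size, 1 − 0.95^15 = 53.7%. The exact size of the uncorrected test at 25 per arm depends on the event rate: 2.0% at an assumed rate of 5%, 5.5% at 20% and 6.5% at 50%. Fifteen independent tests at 6.5% would give 1 − 0.935^15 = 63%. Dependence between outcomes would change these figures again.

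**6. Precision available instead.** The 95% half-width for a risk difference, 1.96 × √(2p(1 − p)/25), is 16.6 points at an assumed p of 10%, 22.2 at 20% and 27.7 at 50%. For a continuous outcome it is t(0.975, 48) × √(2/25) = 0.57 SD. Two-sample t-test power is 41% at 0.5 SD and 79% at 0.8 SD, assuming 25 independent values per arm.

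**The case against.** The strongest reply is that this is a missing label. The outcomes are called secondary, the trial is described throughout as a feasibility study, success is defined only by the 75% criterion, and labelling or multiplicity may be settled in an analysis plan that is not shown. A stated 0.05 threshold is not in itself a claim of efficacy, and questions 1 and 3 are comparative, so tests answer them.

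Much of this stands, and it rules out several stronger readings.

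- A reader might infer that the paragraph contradicts itself. It need not: descriptive summaries can sit beside tests.
- A reader might infer that progression to the multi-centre trial depends on a morbidity p-value. No text says so.
- A reader might take the effects in step 2 as the trial's own. They come from NICU ventilation and from rounded NNTs with wide intervals (10–100, 5–33 and 7–50). Two are composites this trial does not list: mortality and BPD are separate items, and severe brain injury also includes ventriculomegaly. Only pneumothorax matches.
- A reader might take 54% as a ceiling. Step 5 shows that it is not.

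What does not stand is leaving the matter to an analysis plan. The protocol does not leave the point open. It fixes a rule, and an analysis plan could soften it only by departing from the protocol.

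**Conclusion.** The concern holds as a fault in the significance rule. It does not hold as a contradiction between describing and testing. The protocol attaches an unqualified p<0.05 verdict to secondary outcomes and clinical characteristics in a sample described only in terms of feasibility.

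The size is illustrative: power of about 10% to 17% if true effects match the cited NICU figures. On the same assumption, any significant result overstates the effect, on average 2.5 to 3.3 times. The chance of at least one false positive is roughly 54% across 15 tests, given independence and nominal size. The conclusion does not depend on these exact values. The rule is worth changing, but the 75% feasibility decision does not rest on it.

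**What to change.** In the section on statistical methods for primary and secondary outcomes:

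- Keep the descriptive sentence and remove the p<0.05 significance rule for secondary outcomes and clinical characteristics.
- Report each secondary outcome per arm with the between-arm difference and its 95% CI.
- If p-values are kept, for example for workload (question 3), state that they are unadjusted and exploratory and that no secondary outcome will be declared statistically significant.
- Optionally, reword secondary question 1 as estimation of event rates and the difference between arms.

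The change is to wording only, with no effect on data collection or sample size. The cost is that the trial can no longer declare significance on any secondary outcome. That includes workload, where a difference of about 0.8 SD would have been detectable with 79% power.

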The Biostatistics Unit at Women and Children's Health Research Institute (WCHRI), University of Alberta, Edmonton, Canada, will prepare the randomization schedule. Before trial initiation, a statistician will generate the 1:1 allocation sequence with computer-generated random numbers, which a second statistician will independently validate.

Concealment mechanism

The site's allocation sequence is password-protected, with access restricted to the independent statistician.

Implementation

Before the start of the trial, the statistician will use computer-generated random numbers to prepare the allocation sequence by producing the codes and allocation table. Clinical staff attending

Assignment of interventions: blinding

Who will be blinded

Blinding will not be feasible in the delivery room, as the healthcare providers will use two different ventilation devices including the VN 500 Ventilator (VTV-PPV Group) and the Neopuff T-Piece (PPV Group). The outcome assessor will be unaware of the group allocation. This blinding will be maintained until the data is locked for the final analysis, which will be performed blinded to group analysis and then un-blinded.

Procedure for unblinding if needed

Members of the Data Safety Monitoring Board (DSMB) will access unblinded treatment allocations to determine causality for any severe adverse events (SAEs) or other serious trial-related events.

Data collection and management

Plans for assessment and collection of outcomes

The VOLT investigators and research nurses will collect data from maternal and infant paper or electronic medical records. Data will be entered into a REDCap™ (Vanderbilt University) electronic database, designed and managed at the University of Alberta. REDCap is a secure, web-based application that supports data capture for research studies, including database management, survey design, and audit trails to ensure data integrity.

Plans to promote participant retention and complete follow-up

We are anticipating a <5% loss to follow-up until hospital discharge. The center has conducted more than 20 neonatal trials in the delivery room with lost-to-follow-up rates for the primary outcome of <5%.

Data management

VOLT investigators and research nurses will collect maternal and infant data from paper or electronic records and enter it into REDCap™ (Vanderbilt University), a secure, web-based research database designed and managed by the University of Alberta (38, 39).

Confidentiality

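### Secondary clinical outcomes are compared without adjustment for gestational age, which is known for every infant, so outcomes that depend on it are estimated less precisely than the data allow

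*Protocol*

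**What the plan says.** The analysis section fixes the between-arm methods. The sentence that begins "The clinical characteristics and outcome parameters will be compared using Student" goes on to name the t-test, the Mann-Whitney test and chi-square, and no covariate appears. It adds that "The analysis will be 2-sided" and that a p-value "<0.05 will be considered statistically significant". Earlier in the same paragraph, the secondary outcomes are said to be analysed with descriptive statistics.

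Other sections bear on the point:

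- **Sample size:** "We aim to recruit a sample of 50 infants (25 per arm) randomized 1:1 to VTV-PPV or PPV".
- **Sequence generation:** "a statistician will generate the 1:1 allocation sequence with computer-generated random numbers". No stratum, block or minimisation factor is named.
- **Inclusion criteria:** birth between 23+0 and 28+6 weeks' "gestation based on best obstetrical estimates". Gestational age is therefore on record for every infant.
- **Choice of comparators:** lung compliance, and the pressure needed for a suitable tidal volume, are said to differ between infants with gestational age, among other things.
- **Secondary research questions, item 1:** asks whether the intervention reduces severe brain injury, bronchopulmonary dysplasia, severe retinopathy and delivery-room intubation.

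**The concern.** The plan poses a comparative clinical question, sets a significance threshold for it, and answers it with methods that leave out a baseline variable the protocol itself treats as important. The eligible range is six weeks wide. Bronchopulmonary dysplasia is assessed at fixed corrected ages, so an infant born at 23+0 reaches the 36-week assessment 13 weeks after birth, and one born at 28+6 just over 7 weeks after.

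Two things are at stake for outcomes that depend on gestational age. First, variation that the model could explain stays in the error term, so intervals are wider than they need be. Second, if the arms happen to differ in gestational age, the reader has an estimate known to be tilted and no prespecified way to account for it, which invites adjustment after the data have been seen. The trial's results are to inform the design of a larger trial, so clearer estimates have some value even here.

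**Working it through.** The sample size of 50 is given without a derivation, so there is no figure in the plan to reproduce.

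**Inputs from the protocol:** 25 infants per arm; gestational age from 23+0 to 28+6 weeks (a span of 6 weeks); two-sided alpha 0.05; no covariate.

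**Assumptions, because the protocol gives no values:** gestational age spread evenly over the range (a spread skewed to older infants as an alternative); event rates of 30% or 40%; an odds ratio of 1.3 to 2.0 per week at 40% and 1.35 to 2.0 at 30%; R-squared of 0.1 to 0.4 for continuous outcomes.

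**Step 1. Chance imbalance in mean gestational age.**
- SD = 6/√12 = 1.73 weeks.
- SE of the arm difference = 1.73 × √(2/25) = 0.49 week.
- P(difference above 0.5 week, either way) = P(|Z| > 0.5/0.49) ≈ 31%.
- P(difference above 1 week) = P(|Z| > 1/0.49) ≈ 4%.
- With the skewed spread the SE is 0.46 week, and the chances are 28% and 3%.
- By simulation, the arms differ by 5 or more infants in the number born below 26 weeks in 18-20% of trials.

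**Step 2. What a half-week imbalance does to a risk difference.** Shift = 0.5 × (slope of risk on gestational age). The yardstick is the unadjusted SE, √(p(1−p) × 2/25).

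| Event rate | Odds ratio per week | Shift for 0.5 week | Unadjusted SE |
|---|---|---|---|
| 30% | 1.35 to 2.0 | 3.0 to 6.0 points | √(0.21 × 0.08) = 13.0 points |
| 40% | 1.3 to 2.0 | 3.1 to 6.9 points | √(0.24 × 0.08) = 13.9 points |

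The shift is thus about a quarter to a half of one standard error.

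**Step 3. Precision gained by adjustment.** The interval narrows by 1 − √(1 − R²).
- Binary, 40% event rate: R² is 0.047 at an odds ratio of 1.3 and 0.243 at 2.0. The SE falls from 0.139 to 0.135 and 0.121, so intervals are 2% to 13% narrower.
- Two strata (23-25 and 26-28 weeks) recover only part of this. With an even spread, the stratum means lie 1.5 weeks either side of the centre, so strata hold 1.5²/3 = 75% of the variance in gestational age. Applied to the same risk curves, this gives R² of 0.035 to 0.189, and intervals about 2% to 10% narrower.
- Continuous, R² from 0.1 to 0.4: 1 − √0.9 = 5% to 1 − √0.6 = 23% narrower.

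**Step 4. Validity and power of the unadjusted test.** Simulating no treatment effect, with a 40% event rate and an odds ratio of 1.8 per week, the mean risk difference is 0.000. The uncorrected chi-square rejects in 6.0% of trials, close to nominal; the excess reflects small-sample discreteness. Power for 40% v 20% is 0.34 unadjusted and about 0.41 with R² = 0.2. For 40% v 30% it is 0.11 and 0.13.

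**The case against.** The strongest reply is that nothing here is wrong. Unadjusted tests are valid under randomization, and chance imbalance is already part of their standard error. The trial is about feasibility, its secondary analysis is labelled descriptive, and an analysis plan that is not shown could add adjusted results. The gain is modest, rests on assumed inputs, and is smallest for the binary morbidities that the research question names. At 50 infants, sample size is the dominant limit.

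Much of this stands, and it sets the size of the point. Three stronger readings that a reader might infer should be put aside:

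- **That the comparisons are biased or have inflated error.** Step 4 shows that they are not.
- **That every between-arm estimate suffers.** The primary outcome is a percentage judged against 75%, about crossover among infants allocated to the ventilator arm, and is not a between-arm contrast. Nothing in the protocol suggests that operator workload depends on gestational age.
- **That the trial is unstratified.** The protocol is silent on stratification; it does not rule it out.

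What does not stand is that this is merely detail left for later. The protocol names its tests and a threshold for outcome parameters, and asks whether morbidity is reduced. The descriptive label sits in the same paragraph as those tests and does not displace them. Replacing a stated method with a better one, on data already held, is a specific change.

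**Conclusion.** The point holds as a limited improvement to the secondary analysis. It is not a threat to validity or to the feasibility conclusion. For outcomes that depend on gestational age, the stated methods give up some precision: about 2-13% of interval width for binary outcomes if all the gestational-age information is used (about 2-10% with two strata), and 5-23% for continuous ones. In roughly three trials in ten, the arms would differ by more than half a week, which would move a risk difference by 3 to 7 points without a planned way to account for it.

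These sizes depend on the assumed spread of gestational age, event rates and prognostic strength, none of which the protocol gives. Where gestational age is not prognostic, the loss is nil. A reader might also hope that adjustment makes the morbidity comparisons conclusive; on the figures above, it does not.

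**What to change.** Before data lock, state that between-arm estimates of clinical outcomes that depend on gestational age are adjusted for gestational age at birth, with one method per outcome type:

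- **Binary outcomes, where event counts allow:** Mantel-Haenszel risk difference over two strata, 23-25 and 26-28 weeks.
- **Continuous outcomes:** linear regression on gestational age, with log transformation or robust standard errors if the outcome is skewed.

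Report each estimate with a 95% CI and keep the unadjusted results as supportive. List in advance which outcomes are adjusted. One named method per type matters, because alternatives such as Firth logistic regression (a conditional odds ratio) or the van Elteren test (no estimate with an interval) answer different questions.

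The cost is wording and a little more analysis work. Gestational age is already on record, and no visit, procedure or randomization step changes. The small downside is instability for very rare outcomes, which should stay unadjusted. Since the protocol expects recruitment to finish in 2026 and keeps the outcome assessor blinded until data lock, the change can be made before any comparison by arm in the final analysis.
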